After baseline assessment patients will be randomly assigned to receive a neuromuscular exercise programme (control group) or to receive a neuromuscular exercise programme plus a common peroneal nerve EPMN (experimental group). Concealed allocation will be performed using a computer-generated random table of numbers created prior to data collection by an external investigator. Individualised, sequentially numbered index cards will be prepared. These will be placed in sealed opaque envelopes and the second external researcher will open the envelope and proceed with the treatment according to the allocation.

Each group will be treated by a physiotherapist clinician, who will be the principal investigator of the study, with more than 15 years of experience in the management of lower limb

musculoskeletal injuries and more than 10 years of experience in the management of invasive techniques and ultrasound assessment.

The researcher conducting the data processing will be blinded to group membership and the researchers conducting the assessments will be blinded to the participant's group assignment. Participants in this study will not be blinded to their group assignment. All participants will read and sign an informed consent form prior to inclusion in the study and will be asked to lead a lifestyle identical to the one they were leading prior to the start of the study.

4. Procedures:

Neuromuscular exercise programme:

The combination of strength exercise and dynamic balance exercise has been shown to be more effective than strength work alone in the management of CAI (63). The exercise programme applied in the intervention is based on the best available evidence and is common practice in the clinic. All exercises will be performed under the supervision of the therapist. A 3-week intervention will be performed with two sessions per week.

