In addition to the exercise programme, the experimental group will receive a session of EPMN on the common peroneal nerve of the affected lower limb. The EPMN will be applied prior to the exercise programme session. Three interventions will be performed, at a dosage of one per week. It will be performed with the electrostimulator (ES-160 ITO co.). (66) The participant will be placed in prone position with the foot outside the stretcher. The motor part of the common peroneal nerve affecting the innervation of the superficial peroneal nerve will be searched using an ultrasound machine (Chison Echo 5®, Chison Medical Technologies, China) with a high frequency (10 Hz) linear transducer. A dry needle (0.25mmx0.40mm, Agupunt®, Barcelona, Spain) will be introduced until it is close to the perineurium and a square wave biphasic electric current with a frequency of 2 Hz, a pulse width of 250 μ sec and a maximum tolerable intensity will be applied on the needle, with the aim of causing visible muscle contraction, according to the protocol of other studies. (37,42) Ten stimulations with a duration of 10 seconds will be performed, with a rest period of 10 seconds between each stimulation. The needle shall be kept still throughout the procedure and the skin shall be cleaned beforehand with isopropyl alcohol and chlorhexidine.

Assessment and follow-up:

The variables under study will be assessed at 3 different points in time: pre-intervention measurement, post-intervention (one week after the intervention), mid-term measurement (one month after the intervention).

Adverse effects:

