All patients will be asked to report any type of adverse event they may experience throughout the study and up to one month after completion. An adverse event is defined as a sequela of average duration with any symptom perceived as painful or unacceptable by the participant and requiring treatment (67). As needle insertion in some patients may induce post-treatment discomfort, subjects will be advised to report any incidences. EPMN has adverse effects that are infrequent and not serious, such as post-puncture pain that usually lasts from a few hours to a few days of mild intensity, the possible appearance of a haematoma that will be minimised thanks to the use of ultrasound and pressure techniques on the area, nerve irritation that will be minimised as much as possible by the use of ultrasound again and finally the possibility of infection, so a disinfectant will be used on the area before the technique and single-use gloves. The therapeutic exercise programme has subsequently been used by other research groups and is very safe because it is an incremental programme adapted in intensity individually to each

subject. Possible adverse effects are also rare, where the most common may be increased ankle pain, which will be controlled by adapting the load, the possible generation of delayed onset muscle soreness, which usually has a peak duration of 48 hours and a possible fall with instability and disturbance work, which is minimised by the presence of the therapist monitoring the session at all times.

Sample size calculation:

The sample size and power calculation was calculated with the software G-Power 3.1.9.4 (Heinrich Heine Universität Düsseldorf) (68). Calculations were based on the detection of an 8-point mean difference (MCID) on each FAAM scale (46), assuming a standard deviation of 6.5, a 2-tailed test, an Alpha level of 0.05 and a desired power of 90%. The estimated sample size is 15 participants per group.

Statistical analysis of data:

1. Descriptive data in mean, range and standard deviation.
2. Normal distribution/homoskedasticity of the data (See whether the data are parametric or non-parametric). Kolmogorov-Smirnov test and Levene's test.
3. Comparison of means between two groups (experimental group and placebo control group) using Student's t-test to analyse the differences between the quantitative dependent variables of the study. If the data are non-parametric, we will use the Wilcoxon statistic.

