4. Calculate the effect size of the difference between pre and post on the different variables with the cohen's d calculation. A effect size less than 0.2 will be considered trivial, between 0.2-0.5 low, between 0.5-0.8 moderate and greater than 0.8 high.

Data management:

The data will be managed in the following way:

1. Data capture: data will be collected through the data collection notebook which will be obtained by the researcher in charge of the assessments.
2. Classification and storage: each patient will be assigned a control number, in order to maintain the anonymity of the patient over the principal investigator to avoid possible biases. This number will be recorded in a database (Access Sheet) where all patients will be listed in order to identify them in the successive taking of values. This database will

be kept during the execution of the research, and will only be used at the time of data collection, and only the principal investigator of the study will have access to it. Each patient will be identified by this control number and by a code formed by the initials of their first name and their first surname. The data will be stored on the principal investigator's personal computer, access to which is only possible with a username and password available to the same person.

3. Use and treatment: The use is exclusively scientific, without any kind of profit motive. Once the data have been coded, they will be entered into the SPSS statistical package for the corresponding statistical calculation, which will be carried out by the researcher in charge of the analysis. In the dissemination of the results there will be absolute confidentiality of the participant's personal data.
4. Assignment and transfer of data to a third party for processing: No data will be transferred to a third party for processing.
5. Destruction: the data in the collection notebook will be destroyed by a paper shredding machine and the data in the database will be kept for a maximum period of 10 years, after which it will be completely deleted from the researcher's personal computer.

Ethical considerations:

All participants will receive information on the main aspects of the study and will be asked to complete an informed consent form in accordance with applicable law. The procedures to be carried out in this study will follow the ethical standards of the Declaration of Helsinki.

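### The between-group test in item 3 fixes neither the score analysed nor any use of the baseline value, so precision is generally lost and two different tests are permitted

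*Combined protocol and SAP*

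**What the plan says.** Under Randomisation, the baseline is taken before allocation: "After baseline assessment patients will be randomly assigned to receive a neuromuscular exercise programme (control group". Under Assessment and follow-up, "The variables under study will be assessed at 3 different points in time": before the intervention, one week after it and one month after it. Each outcome therefore has a pre-randomisation value.

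The only between-group inference is item 3 of Statistical analysis of data, which compares the two groups "using Student's t-test to analyse the differences between the quantitative dependent variables of the study". The alternative is "If the data are non-parametric, we will use the Wilcoxon statistic". Item 3 names no score (follow-up or change), no visit and no covariate. Item 4 does mention change, but only for Cohen's d: "Calculate the effect size of the difference between pre and post on the different variables". No ANCOVA, regression or mixed model appears anywhere in the document.

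The sample-size section targets an 8-point FAAM difference, "assuming a standard deviation of 6.5, a 2-tailed test, an Alpha level of 0.05 and a desired power of 90"%, and arrives at 15 per group. It does not say whether 6.5 is the SD of scores at one time point or the SD of change.

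**The concern.** With 15 per arm, chance imbalance at baseline is not small. If 6.5 is the SD at one time point, the baseline group difference has a standard error of 2.37 points, against a target effect of 8.

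Assume equal SDs at both times and let r be the correlation between baseline and follow-up. A test on follow-up scores carries r times the baseline imbalance into the estimated effect. A test on change scores carries (r − 1) times it. At r = 0.5, an imbalance of one standard error moves the two estimates by about 1.2 points in opposite directions. ANCOVA removes this on average and generally gives a narrower interval.

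The second problem is that the analysed score is open. Two analyses both satisfy item 3, they can reach different verdicts on the same data, and the plan does not say which one counts.

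**Working it through.** **Inputs from the sample-size section:** difference 8, SD 6.5, two-sided alpha 0.05, power 90%, n = 15 per arm.

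**Assumed, because the documents do not give them:** r, taken as 0.3, 0.5 and 0.7; equal SDs at baseline and follow-up; normal data; and two readings of the SD. In reading A, 6.5 is the SD at one time point. In reading B, 6.5 is the SD of change.

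**1. The plan's own figure.** SE = 6.5 × √(2/15) = 2.373. With 28 df the critical t is 2.048, so the half-width is 2.048 × 2.373 = 4.86. Noncentral t power at 15 per group is 90.2%, and at 14 it is 88.0%. The stated 15 per group is correct for an unadjusted t-test.

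**2. Formulas.** Let SD₁ be the SD at one time point.
- Follow-up-score t-test: SE = SD₁ × √(2/15), 28 df.
- Change-score t-test: SE = SD₁ × √(2/15) × √(2(1 − r)), 28 df.
- ANCOVA: SE = SD₁ × √(2/15) × √((1 − r²)(1 + 1/26)), 27 df. The factor 1 + 1/26 is the expected small-sample cost of estimating the slope with N = 30, that is 1 + 1/(N − 4).

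In reading A, SD₁ = 6.5. In reading B, SD₁ = 6.5/√(2(1 − r)), which is 5.49, 6.50 and 8.39 at the three values of r.

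Example at r = 0.5: ANCOVA SE = 2.373 × √(0.75 × 27/26) = 2.095, and half-width = 2.052 × 2.095 = 4.30.

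**3. Power at 15 per arm, with the ANCOVA half-width.**

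| Reading | r | Follow-up t-test | Change t-test | ANCOVA | ANCOVA half-width |
|---|---|---|---|---|---|
| A | 0.3 | 90.2% | 78.5% | 91.6% | 4.73 |
| A | 0.5 | 90.2% | 90.2% | 95.7% | 4.30 |
| A | 0.7 | 90.2% | 98.7% | 99.4% | 3.54 |
| B | 0.3 | 97.0% | 90.2% | 97.7% | 4.00 |
| B | 0.5 | 90.2% | 90.2% | 95.7% | 4.30 |
| B | 0.7 | 71.2% | 90.2% | 93.3% | 4.58 |

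The t-test that matches the SD reading always has half-width 4.86. Simulation with 200,000 trials per setting gives the same ANCOVA power to within 0.1 percentage point.

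**4. Where the gain ends.** Against follow-up scores, ANCOVA gains nothing at r of about 0.20 or below; at r = 0 its power is 89.0% against 90.2%. Against change scores, the variance ratio is (1 + r)/2 × 27/26, and after the lost degree of freedom the gain ends at r of about 0.92.

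**5. Cost of the open score, by simulation.** With a true 8-point difference, the follow-up and change t-tests disagree on significance in the following share of trials:

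| Reading | r = 0.3 | r = 0.5 | r = 0.7 |
|---|---|---|---|
| A | 19–20% | 14% | 10% |
| B | 10% | 14% | 28% |

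With no effect, each test alone rejects in about 5% of trials and the two disagree in 8% to 9%. The chance that at least one rejects is (sum of the two rates + disagreement)/2. At r = 0.5 this is (0.050 + 0.050 + 0.083)/2, about 9%; at r = 0.3 and 0.7 it is also about 9%.

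**The case against.** The strongest reply is that nothing here is an error. The t-test is valid under randomisation, and the plan meets its own power target with the test it names. That stands: the point concerns efficiency and specification, not bias or sample size.

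A second reply is that change scores are implied, since the stated hypothesis speaks of larger improvement in the combined group and item 4 takes Cohen's d on pre-post differences. These do point towards change, but they do not define the variable tested in item 3. If change is meant, ANCOVA is still more precise below r of about 0.92, and under reading A with r = 0.3 the change-score test falls to 78.5% power.

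Third, the gain may be small. The FAAM test-retest values of 0.89 and 0.87, given with the scale's description, are a rough ceiling for r. Near it, under reading B, ANCOVA has only 90.9% power at r = 0.87 against 90.2%, with half-width 4.80 against 4.86. This is right, though the FAAM and pain entry thresholds may lower r in this sample. FAAM percentages are also bounded, so calculations based on normality are approximate.

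Finally, the 9% type I error needs someone to run both tests and report the favourable one. Nothing in the plan proposes that, and the person processing the data is to be blinded to group. Blinding does not prevent selection by p-value, but the 9% describes what the wording leaves possible, not what is planned.

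**Conclusion.** The concern holds. Item 3 leaves the tested score undefined and never uses the pre-randomisation value as a covariate. That both statements are true is clear from the text. The size of the loss is not known, because r and the meaning of 6.5 are missing. For r between 0.3 and 0.7, ANCOVA adds roughly 1 to 9 percentage points of power over the t-test that matches the SD reading (91.6% to 99.4% against 90.2%). Against the t-test that does not match it, the gain reaches about 22 points (93.3% against 71.2%, reading B at r = 0.7). Outside that range the gain can shrink to nothing or become a very small loss. The ambiguity matters separately, because the two permitted tests would often disagree. This should be corrected before analysis, but it does not invalidate the design.

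**What to change.** Replace item 3 with wording to this effect:

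> For each quantitative outcome, separately at one week and at one month, the follow-up score will be analysed by ANCOVA with treatment group and the baseline value of the same outcome as the only terms. The adjusted group difference will be reported with its 95% confidence interval, in all randomised participants with data at that visit, analysed as randomised.

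The switch to Wilcoxon after a preliminary Kolmogorov-Smirnov or Levene check then falls away. Inspect the ANCOVA residuals instead; a permutation test of the adjusted difference can serve as a sensitivity analysis. In the sample-size section, state whether 6.5 is the SD at one time point or the SD of change.

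The cost is SAP wording. Baseline values are already collected, ANCOVA uses one degree of freedom and runs in SPSS, which the plan already names, and 15 per group need not change. The permutation test may need a short script. This change does not settle which outcome and visit are primary; that has to be stated separately.

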In terms of function, after the development of CAI, 72% of people do not return to their pre-injury level of physical activity and 6% are unable to return to work (10). In this regard, there are different instruments to assess function in the foot/ankle complex, but only two have been suggested by the International Ankle Consortium to assess functional limitations in patients with CAI: the Foot and ankle ability measure (FAAM) and the Foot and ankle Outcome score (FAOS) (20). Although these measures are subjective and based on individual perception of the person's condition, they are very useful in the research setting as they provide important information regarding physical and functional limitation in the context of CAI.

Conservative treatment is the initial therapeutic option for patients with CAI, however, the best strategies are still unclear. Numerous rehabilitation protocols to improve deficits associated with CAI have been examined. These range from simple progressive strength work (21-24) or dynamic postural balance protocols (25-28) to multicomponent rehabilitation approaches

(strength, balance, mobility) (29,30) with effective results in improving strength, balance and function (21-24,28,30-36).

Clinically, a new invasive technique has appeared, known as Percutaneous Ecoguided Neuromodulation (EPMN). This minimally invasive intervention consists of the application of percutaneous electrical stimulation (biphasic square wave electrical current) through an acupuncture needle, as an electrode placed in the vicinity of the nerve or motor point of the muscle to be treated under ultrasound guidance (37), which is hypothesised to generate structural and excitation changes in the nerve, resulting in decreased sensitisation of the nerve. It is an accessible, safe and cost-effective technique for physiotherapists to treat musculoskeletal conditions. To date, there is limited evidence regarding its use. EPMN has been applied for different pathologies with good therapeutic results (38-42), but its use in combination with a multicomponent neuromuscular exercise programme has never been studied.

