Therefore, the main objective of the study will be to compare the short- and medium-term effects of an EPMN intervention on the common peroneal nerve together with an exercise programme in relation to pain, ankle range of motion, ankle muscle strength, dynamic balance and function in both performance and self-report in patients with CAI. We hypothesised that those patients who receive neuromodulation combined with the neuromuscular exercise programme will have greater improvements in relation to the variables studied than those subjects who only receive the neuromuscular programme.

METHODOLOGY:

1. Participants:

Adult volunteers from the student body of the Escuela Universitaria Gimbernat Cantabria with a history of ankle sprain and physically active, defined as participation in moderate aerobic physical activity of at least 30 minutes 5 days a week, or vigorous intensity aerobic activity of at least 20 minutes 3 days a week (43), will be assessed to see if they can participate and be included in the study (44).

Inclusion Criteria: Subjects must meet the criteria:

1. History of at least one major ankle sprain. The initial sprain must have occurred at least 12 months prior to study participation, be associated with inflammatory symptoms (pain, oedema) and have resulted in at least one day of interrupted physical activity.
2. The most recent sprain must have occurred at least 3 months prior to study participation.
3. History in the injured ankle of "ankle wandering" (at least 2 episodes in the 6 months prior to study participation) and/or repeated sprains (two or more sprains in the same ankle) and/or feelings of instability in activities of daily living or sports (score less than 24 on the Cumberland Ankle Instability Tool (CAIT)).
4. Have a score of less than 75% in three or more categories on the FAOS (Foot and ankle Outcome Score) or a level of less than 90% in activities of daily living or a level of less than 80% in sports activities on the FAAM (Foot and ankle ability measure).
5. Pain on the VAS scale above 3 points out of 10 in physical activity.

Patients will be excluded from the study if they exhibit any of the following criteria:

1. History of surgery on either lower extremity that may interfere with the performance of the tests.
2. History of a fracture of either lower extremity requiring alignment.

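### The only planned effect size is a pre-to-post Cohen's d, which counts improvement shared by both arms and does not measure what EPNM adds to exercise

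*Combined protocol and SAP*

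**What the plan says.** The section on statistical analysis has four items: descriptive statistics (mean, range, SD), distribution checks, a two-group test, and an effect size.

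- Item 3: "Comparison of means between two groups (experimental group and placebo control group) using Student's t-test", with a Wilcoxon test as the fallback. (The control arm receives exercise alone; no placebo is described.)
- Item 4: "Calculate the effect size of the difference between pre and post on the different variables with the cohen's d calculation". It is then graded: "A effect size less than 0.2 will be considered trivial, between 0.2-0.5 low, between 0.5-0.8 moderate and greater than 0.8 high".

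No other effect estimate is planned. The confidence intervals in the document concern the validity and reliability of the instruments, not the treatment effect.

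Four other places bear on this:

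- Introduction, hypothesis: "We hypothesised that those patients who receive neuromodulation combined with the neuromuscular exercise programme will have greater improvements" than those given exercise only.
- Randomisation: participants are "randomly assigned to receive a neuromuscular exercise programme (control group) or to receive a neuromuscular exercise programme plus a common peroneal nerve EPMN". Both arms therefore exercise.
- Introduction, on conservative treatment: earlier rehabilitation programmes are described "with effective results in improving strength, balance and function".
- Assessment and follow-up: after baseline there are two visits, "post-intervention (one week after the intervention), mid-term measurement (one month after the intervention").

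**The concern.** The hypothesis and the sample size concern a difference between arms. The planned magnitude, as worded, concerns a difference between visits. On the plan's own premise that exercise works, both arms should improve. A pre-to-post d includes that improvement, whereas a between-arm contrast cancels it.

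A reader of the results would therefore have a p-value for the comparison of interest, no planned estimate or interval to go with it, and a graded effect size that answers a different question. A *high* grade in the experimental arm could be taken as evidence for EPNM when it reflects exercise, practice with the tests or regression to the mean. The SD is also undefined, so the same data can yield different values of d. Finally, item 4 speaks only of pre and post, and the follow-up section uses post-intervention for the one-week visit. The medium-term effect, which is part of the main objective, is left without a stated effect size.

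**Working it through.** **Inputs from the plan.** Difference of 8 points on each FAAM scale, SD 6.5, two-tailed alpha 0.05, power 90%, 15 per group (Sample size calculation); *high* means d above 0.8 (item 4).

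**Assumptions, not in the plan.** SD 6.5 applies at each visit; pre-post correlation r from 0.3 to 0.7; a gain shared equally by both arms of 3.25, 5.2 or 8 points; no added EPNM effect.

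**1. The plan's own figure.** d = 8/6.5 = 1.23. A two-sample t-test (noncentral t) has power 0.880 at 14 per group and 0.902 at 15, so the stated 15 is reproduced. A paired pre-post calculation with a change SD of 6.5 would need only 10 (9.07 rounded up). The trial was therefore sized on the between-arm contrast.

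**2. What each d measures.** Let c be the shared gain and a the added effect of EPNM. Using SD 6.5:

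- control arm, pre-post: d = c/6.5
- experimental arm, pre-post: d = (c + a)/6.5
- between arms: d = a/6.5

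With c = 8 and a = 0, both arms have a pre-post d of 1.23 (*high*), while the between-arm d is 0.

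**3. Shared gain at which the true d is *high* although a = 0.**

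- Average of the visit SDs: 0.8 × 6.5 = 5.2 points.
- SD of change: 0.8 × 6.5 × √(2(1 − r)) = 6.15, 5.20 and 4.03 points at r = 0.3, 0.5 and 0.7.

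**4. How often the sample d is *high* in both arms when a = 0.** Simulation of 200,000 pairs of arms, 15 per arm; the three figures are for r = 0.3 / 0.5 / 0.7.

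| Shared gain | Average SD | SD of change |
|---|---|---|
| 8 points | 0.832 / 0.882 / 0.935 | 0.647 / 0.867 / 0.992 |
| 5.2 points | 0.260 / 0.261 / 0.273 | 0.128 / 0.269 / 0.635 |
| 3.25 points | 0.034 / 0.024 / 0.012 | 0.012 / 0.029 / 0.103 |

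**5. Effect of the undefined SD.** The same 8-point change gives d = 1.23 on SD 6.5, but 1.04, 1.23 and 1.59 on the SD of change at r = 0.3, 0.5 and 0.7.

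**6. The interval that is not planned.** Half-width of the 95% CI for the group difference at 15 per arm, r = 0.3 / 0.5 / 0.7:

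- change scores: t₂₈ × 6.5 × √(2(1 − r)) × √(2/15), with t₂₈ = 2.048, gives 5.75 / 4.86 / 3.77 points;
- baseline-adjusted: t₂₇ × 6.5 × √(1 − r²) × √(2/15), with t₂₇ = 2.052, gives 4.65 / 4.22 / 3.48 points.

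Against a target of 8 points, this uncertainty is large enough that a reader needs to see it.

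**The case against.** The strongest reply is that item 4 may mean something else. It follows directly on the two-group comparison and names no arm, and the hypothesis is about greater improvement. The pre-post difference may simply be the variable compared between groups, in which case d would be the right quantity. That reading is possible, but the text does not state it, and under it the contrast, the SD, the time points and the interval would still be missing.

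A second reply concerns size. The document gives no figure for the shared gain. The programme has six sessions over three weeks, shorter than several of the cited four- and six-week programmes, and a shared gain of 8 points equals the whole planned between-arm difference. At 3.25 points, both arms are *high* in at most about 10% of trials. Moreover, *high* in both arms beside a null test may mislead few readers. The more misleading result is *high* in the experimental arm only, with no added effect. Under the same assumptions that occurs in 3–8% of trials (average SD) or 0.4–16% (SD of change) at a gain of 8, in about 25% or 16–25% at 5.2, and in 10–15% or 10–22% at 3.25. These points change the size and pattern of the problem, but not its direction.

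Third, the plan does not say whether 6.5 is the SD at a visit or of change. If it is the SD of change, the threshold on that SD is 5.2 points and the change-score half-width is 4.9 points, whatever r is. The conclusion is the same.

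Fourth, item 1 supplies means and SDs. If these are reported by arm, a raw difference can be derived. However, the interval for a difference in change needs the SD of change, which visit SDs do not give without r.

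**Conclusion.** The concern holds. As written, the plan's only effect size does not estimate the added effect of EPNM, and no between-group estimate with an interval is planned at either follow-up visit. The structural point rests on no assumption: any shared gain enters a pre-post d and cancels from a between-arm one. How often a misleading grade would result depends on the assumed shared gain and correlation, and ranges from about 1% to 99% for *high* in both arms over the scenarios shown. The item 3 test and the 15 per group are unaffected. The fault lies in estimation and interpretation, and it should be corrected before the data are analysed.

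**What to change.** Replace item 4 as follows.

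- For each outcome, at one week and at one month, report the between-group difference in change from baseline with a 95% CI. A baseline-adjusted difference is an alternative; if it is chosen, align item 3 so that the test and the estimate match.
- Add a between-group standardised effect with its SD defined and its own CI, and apply the trivial-to-high bands to that effect only.
- Read the raw difference against the MCIDs that the plan already gives: FAAM 8 (daily living) and 9 (sports), CAIT 3, NPRS 1.5–2.1. The plan uses only the 8 FAAM points as a group difference, and it describes the NPRS values as changes, so the latter are a guide rather than a criterion.
- Keep pre-to-post change within each arm as description, without grades.

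If item 4 was meant as a between-group d of change, say so and state the contrast, the SD and the time points.

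The cost is rewording item 4, possibly aligning item 3, and a little more analysis. The reported magnitudes will carry wider intervals and will probably look less favourable. No extra participants or visits are needed.

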3. Acute injury to the musculoskeletal structures of other joints of the lower extremity within the previous 3 months, which impacts joint integrity and function resulting in at least one day of loss of physical activity.
4. Chronic concomitant pathology of the lower extremity (e.g. osteoarthritis, vascular disease, neural pathology).
5. Regular use of antalgic medication that may mask symptoms.
6. Contraindications to percutaneous puncture and to the performance of neuromodulation.
7. Receiving physiotherapy or medical treatment during the operation.
8. Being pregnant at the time of the start of the study.

2. Variables to be studied

2.1 Self-administered scales:

- **The Foot and ankle ability measure (FAAM)**, validated in Spanish (45), is a Likert scale consisting of 29 items, which have a score from 0 to 4, representing different levels of difficulty, divided into two subscales: activities of daily living (ADL) (21 items) and sports (8 items). The values are summed to calculate the score for each subscale, 84 points for ADLs and 32 points for sports (45). For the analysis of the score, the percentage of each subscale is used separately. The test-retest reliability is high, 0.89 for the ADLs and 0.87 for the sports subscale. In fact, the FAAM scale has been shown to be valid for use in patients with ankle instability. (46) It has been suggested that the minimum clinically important difference (MCID) is 8 and 9 points for the ADL subscale and for the sports subscale, respectively. (47)

- **The Cumberland Ankle Instability Tool (CAIT)**, validated in Spanish (48), has been shown to be a valid and reliable tool for assessing functional ankle instability (49). With an intraclass correlation coefficient (ICC) of 0.96, the CAIT scale has demonstrated excellent test-retest reliability. The scale consists of 9 items with a maximum score of 30 points, where higher scores indicate greater stability. It has been suggested that the MCID is 3 or more points (50).

2. 2 Measurements carried out by the therapist:

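### Item 4 grades results by generic Cohen's d bands with no confidence interval and no use of the cited MCIDs, so a FAAM result below the MCID can be labelled 'high'

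*Combined protocol and SAP*

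**What the plan says.** Under 'Statistical analysis of data', items 1 to 3 cover descriptive statistics, distribution checks and a two-group comparison by Student's t-test or a Wilcoxon statistic. Item 4 adds the effect size: "Calculate the effect size of the difference between pre and post on the different variables with the cohen's d calculation". The labels follow: "A effect size less than 0.2 will be considered trivial, between 0.2-0.5 low, between 0.5-0.8 moderate and greater than 0.8 high". Item 4 does not say which SD standardises d, and none of the four items mentions a confidence interval or an MCID.

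Elsewhere the protocol does work with MCIDs. The FAAM entry in section 2.1 reports that the "minimum clinically important difference (MCID) is 8 and 9 points for the ADL subscale and for the sports subscale, respectively". Section 2.1 also gives 3 or more points for the CAIT, and the NPRS entry in section 2.2 gives 1.5 to 2.1 points. 'Sample size calculation' is built on an "8-point mean difference (MCID) on each FAAM scale (46), assuming a standard deviation of 6.5, a 2-tailed test", with alpha 0.05 and power 90%, and concludes: "The estimated sample size is 15 participants per group".

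**The concern.** The trial is sized on a difference expressed in FAAM points, but its results are put into words on a scale that takes no account of that difference. If the top band opens below the MCID, a change or difference too small to meet the protocol's own benchmark can be reported as a 'high' effect, with nothing in the planned output to correct the impression.

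Two features add to the risk. First, item 4 is a pre-post effect size. Both arms receive the exercise programme (section 3, 'Randomisation'), so a within-arm pre-post d includes the exercise effect and can be 'high' whatever the neuromodulation adds. Second, without an interval a non-significant comparison says nothing on whether an MCID-sized benefit has been ruled out.

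**Working it through.** **Inputs.** Difference 8 points, SD 6.5, two-sided alpha 0.05, power 90% and 15 per group (all 'Sample size calculation'); MCIDs of 8 and 9 (section 2.1, FAAM); band limits 0.2, 0.5 and 0.8 (item 4). The document does not say whether 6.5 is the SD of scores or of change.

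**1. The plan's own figure.** The standardised difference is 8 / 6.5 = 1.23. The exact two-sample noncentral-t calculation gives power 0.880 at 14 per group and 0.902 at 15. The stated 15 per group is reproduced, and nothing below changes it.

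**2. Bands in FAAM points, if d is standardised by 6.5** (points = d x SD):
- 'low' starts at 0.2 x 6.5 = 1.3
- 'moderate' starts at 0.5 x 6.5 = 3.25
- 'high' starts at 0.8 x 6.5 = 5.2

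The MCIDs correspond to d = 8 / 6.5 = 1.23 (daily living) and 9 / 6.5 = 1.38 (sports). The 'high' cut-off is 5.2 / 8 = 65% of the first and 5.2 / 9 = 58% of the second.

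**3. Dependence on the standardiser.** The cut-off is 0.8 x SD. It is below 8 points for any SD under 8 / 0.8 = 10, and below 9 points for any SD under 9 / 0.8 = 11.25. For assumed SDs of 5, 8, 10 and 12 it is 4.0, 6.4, 8.0 and 9.6 points.

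The two pre-post conventions move it in opposite directions as the pre-post correlation r rises. The document gives no such r, so the values are assumptions.

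| Assumed r | 6.5 is the score SD; d uses the change SD: 5.2 x sqrt(2(1-r)) | 6.5 is the change SD; d uses the baseline SD: 5.2 / sqrt(2(1-r)) |
|---|---|---|
| 0.3 | 6.2 | 4.4 |
| 0.5 | 5.2 | 5.2 |
| 0.7 | 4.0 | 6.7 |
| 0.8 | 3.3 | 8.2 |
| 0.89 | 2.4 | 11.1 |

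Under the first convention the cut-off cannot exceed 5.2 x sqrt(2) = 7.35 points for any non-negative r. Under the second it passes 8 points once r exceeds 1 - (5.2/8)^2 / 2 = 0.79, and 9 points once r exceeds 1 - (5.2/9)^2 / 2 = 0.83.

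**4. Between-arm illustration** (SD 6.5, 15 per arm). These figures describe the item 3 contrast, not the pre-post d of item 4.
- The smallest significant difference, which is also the 95% CI half-width, is t(0.975, 28) x 6.5 x sqrt(2/15) = 2.048 x 2.373 = 4.86 points. A result can therefore be significant, have d above 0.8 and still fall below 8 points.
- The probability that a between-arm d exceeds 0.8 is 32%, 48% and 63% at true differences of 4, 5 and 6 points. By simulation, d exceeds 0.8 while the observed difference is below 8 points in 27%, 37% and 43% of trials.
- An observed 4.5 points is not significant, yet its interval is 4.5 ± 4.86, or about -0.4 to 9.4, which includes the MCID.

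**5. A stricter rule that might be proposed.** Suppose benefit is declared only when the interval excludes 0 and the estimate reaches 8 points. At a true 8-point difference the estimate falls below 8 about half the time, so the rule succeeds in about 50% of trials (simulation), against 90% for the t-test.

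**The case against.** The strongest reply is that nothing here is contradictory. The bands describe standardised size for every outcome, including hop time, jump height, strength and range of motion, and conventional labels beside a t-test are ordinary practice. The protocol reports the FAAM MCIDs only as suggested values. That stands: a reader might infer that the plan would declare a gain below the MCID clinically important, but nowhere does it say that 'high' means important.

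A reader might also take 5.2 points as a threshold in the plan, or conclude that the mismatch persists whichever contrast or SD is used. Neither is supported. The bands are in SD units, item 4 names no standardiser, and d will use an observed SD. If 6.5 is a change SD and d is divided by the baseline SD, the mismatch for daily living disappears once r exceeds about 0.79. In that case the t-test on change also keeps its 90% power, so it is not generally true that the bands and the MCID can agree only if the sample-size assumption fails. Power does fall to 56% if the SD of 10 at which they agree applies to the between-arm comparison as well.

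Finally, the SD of 6.5 and the 8 points were set for a between-group comparison, whereas item 4 is pre-post. The probabilities in step 4 are illustrations and not properties of item 4.

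What the reply does not remove is the gap itself. The plan offers no other verbal scale of magnitude, no interval and no comparison with the MCIDs it cites.

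**Conclusion.** The concern holds as a risk of misleading interpretation, not as a calculation error or an internal contradiction. If the plan's only FAAM SD standardises d, results above 5.2 and below 8 points (below 9 for sports) would be labelled 'high' while falling short of the MCID. The direction holds for any standardising SD under 10 (11.25 for sports); the exact cut-off depends on a standardiser the plan does not name.

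The numerical case is for FAAM only, because the document gives no SD for CAIT or NPRS. The absence of any MCID comparison applies to all three. The figures also assume that 8, 9 and 6.5 share one unit. Section 2.1 describes subscale totals of 84 and 32 points but analyses percentages, and does not say which unit the MCIDs use. The sample size is unaffected.

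**What to change.** For FAAM, CAIT and NPRS, replace the verbal bands in item 4 with the between-arm mean difference and its 95% CI, shown beside the MCID already cited. State whether FAAM values and MCIDs are in points or percent. Say in words whether the interval includes or excludes the MCID. If d is kept for these outcomes, report it without a label and name its contrast and its standardising SD.

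Do not add a rule requiring the estimate to reach the MCID: step 5 of the working shows it would fail in about half of trials at the very difference the study was sized to detect.

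The change takes one paragraph of analysis wording and no new data. The downside is that some results lose a favourable label.
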